3. **2nd measurement ('Beginning of treatment') and randomisation.** During the initial interview, the treating psychologist provides oral information about the research project and hands over further written participant information and a consent form. The treating psychologist points out that the client has one week to decide whether S/he wishes to participate in the research project and that s/he can withdraw his/her consent at any time. The client is informed that s/he will be offered other relevant treatment by the MPD, if s/he does not wish to participate in the research project. If the client wishes to participate in the research project and the therapist assesses that, based on the initial interview, the client meets the inclusion criteria, the psychologist initiates the 2nd measurement ('Beginning of treatment'), involving a questionnaire package that the client is to fill in on a tablet. The questionnaires of the 2nd measurement are presented in Table 2 and are further described in the section 'Evaluation and Effect Analysis'. To complete the client's response to the 2nd measurement, the random allocation of the client for either intervention (MPC) or control treatment (MPC without co-decision) is automatically carried out on the tablet, as described in the 'Randomisation' section.
4. After that, either intervention (MPC) or control treatment (MPC without co-decision) is carried out as prescribed in the treatment manual.
5. **3rd measurement ('Continuous process and effect evaluation').** After each treatment module including the intro module (see detailed description of the MPC treatment programme below), a brief assessment is conducted. This includes four questionnaires as shown in Table 2. The client completes these questionnaires on the tablet, and the client and therapist automatically receive a response as to whether the client still suffers from C/PTSD, based on the ITQ (primary outcome measure). When the therapist and client decide to end the treatment, the therapist asks the client to complete the final questionnaires (4th measurement) on the tablet.
6. **4th measurement ('End of treatment').** At the end of treatment (see description below) the 4th measurement ('End of treatment') is completed on the tablet.
7. **5th measurement ('3-month follow-up').** Three months after completing the 'End of treatment' assessment, the client will receive a questionnaire package in their e-Boks as a three-month follow-up assessment.

Record keeping

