The treatment is registered in COSMIC (the record keeping system used at the MPD). Treatment record is used for treatment sessions, and the treatment ends with a concluding record.

Supervision

The participating therapists receive method-specific supervision in MPC every 14 days by supervisors [name] and [name], who have been involved in the development of the treatment programme. In addition, all therapists receive supervision in Trauma-Focused Cognitive Behavioral Therapy on a monthly basis, as part of the regular routine at the MPD.

Evaluation of treatment effects

A thorough effect evaluation of the MPC treatment programme will be carried out with questionnaires completed by the clients before, during and after the treatment. In addition, the therapeutic process will be evaluated with questionnaires completed by the client after each treatment module.

Table 2 provides an overview of all measurement times and questionnaires used for the process and outcome assessment of the MPC treatment programme.

Questionnaires	Num- ber of items	Time of admin- istration (minutes)	Measurement times				
			Before treatment 1st measurement 'Baseline' (package of question- naire is sent to the cli- ent's e-Boks as part of the regular procedure at the MPD)	During treatment 2nd measurement 'Beginning of treat- ment' Questionnaire package is completed on tablet before randomisation and first therapy ses- sion	3rd measurement 'Continuous process and effect evaluation' ^a Four questionnaires are completed after each treat- ment module	After treatment 4th measurement 'End of treatment' Questionnaire package is completed on tablet after last therapy session	3-month follow-up 5th measurement '3-month follow-up' (questionnaire package is sent to the client's e-Boks)
Demographic in- formation	5	2:23	X			X	X
Suicidal thoughts and behaviour	4	0:35	X			X	X
Prior treatment	7	0:52	X				
Medicine	2	0:22				X	X
TLEQ	23	7:33	X			X	X
DASS-42	42	2:50	X			X	X
ITQ	20	2:49	X	X	X	X	X
PCL-C	17	1:49	X			X	X
ADRS	6	0:48	X				
Alcohol intake	3	1:02	X			X	X
Drugs	7	0:49	X			X	X
WHO-5	5	1:02	X	X		X	X
SDS	3	1:01	X	X		X	X
ACE	25	5:40		X			
ISI	7	1:40		X		X	X
CMDQ	12	2:58		X		X	X
ECR-S	12	2:24		X		X	X
Social support	12	2:20		X		X	X
Other help and support	10	2:00				X	X
CMTS	24	2:38			X		
SAI	6	0:44			X		

Number of items	142	106	57	237	184
Estimated use of time (minutes)	24	20	7	30	34

Table 2. Overview of measurement times and questionnaires

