Note: ^a Note that measurement 3 occurs after each treatment module (including the intro module) and is thus carried out several times (depending on the length of the client's course of treatment).

TLEQ = Traumatic Life Events Questionnaire; Dass-42 = Depression Anxiety Stress Scales; ITQ: International Trauma Questionnaire (primary outcome measure); PCL-C = Posttraumatic Stress Disorder Checklist - Civilian Version; ADRS = ADHD Symptom Checklist for Children - The Adult Self Report Symptoms of Childhood Scale; WHO-5 = WHO-Five Well-being Index; SDS = Sheehan Disability Scale; ACE = The Adverse Childhood Experiences questionnaire; ISI = The Insomnia Severity Index; CMDQ = item 1-12 from the Common Mental Disorders Questionnaire; ECR-S = The Experiences in Close Relationships - Short Form; CMTS: Client Motivation for Therapy Scale; SAI = Session Alliance Inventory

Measures

See Table 2 for an overview of measurement times.

Demographic information. Five questions examine the client's gender, age, marital status, job position and children.

Suicidal thoughts and behaviour are assessed with four questions regarding suicidal thoughts, plans and previous suicide attempts. Two questions are to be answered on a 5-point scale from 'Never' to 'Very Often', examining suicidal thoughts and plans in the last six months. Two others are to be answered with 'Yes/No', examining suicide attempts in the last year and before that. The four questions have been used in EPSIS, the WHO study ('Euro Multicentre Study of Suicidal Behavior') as well as national surveys (SuSY, the National Institute of Public Health, University of Southern Denmark) and in studies by the Danish Centre for Suicide Research.

Previous treatment and medication. Previous treatment is assessed with five questions that examine whether the client has received treatment in the past due to psychological or psychiatric problems, whether the client has been diagnosed and whether the client is still in treatment. Medication is assessed with two questions, asking whether the client has received any prescription or nonprescription medicines in the last 14 days, and if so, what the medicine is called.

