4. STATISTICAL CONSIDERATIONS

Number of subjects

Strength calculation is not required for pilot studies for Phase III trials and is in some cases even advised against (Billingham et al., 2013; Thabane et al., 2010). Based on comparable feasibility studies on testing new treatment methods for clients with PTSD (Mahoney et al., 2020; Scharff et al., 2020), we have estimated that 30 participants in the intervention and 30 in the control group are required for a representative sample.

Statistical analysis

Data from this pilot study will help provide information for a future efficacy RCT (Phase III trial) by testing the trial procedures. Therefore, no formal statistical analysis of data from the pilot study will be carried out. A description of the participants and a simple compiling of pilot data will be presented. Exploratory analyses will be conducted to compare means (and 95% confidence intervals) of the ITQ and the other secondary outcome measures between intervention and control group at the end of the treatment using a t-test. Furthermore, repeated measurements within the same group will be analysed using variance analysis (ANOVA). All randomised participants will be included in the analyses. The statistical analyses of pilot data will only be exploratory since the sample size does not allow for definitive analyses.

We will consider the study as complete if the following success criteria are met:

1. > 70% of potential participants accept and be included in the study

2. Completion rate of 70%, that is, we expect to have complete data (Measurement 4, completed at the final therapy session) of at least 70% of all participants included
3. Complete three-month follow-up (Measurement 5, obtained via e-Box) of at least 50% of all participants included

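### The plan says all randomised participants are analysed, but its t-test and ANOVA use only available scores, and clients who stop attending have no stated route to Measurement 4 or date for Measurement 5

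*Combined protocol and SAP*

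**What the plan says.** Section 4 (Statistical analysis) plans exploratory comparisons of means with 95% confidence intervals between the arms at end of treatment by t-test, and within-group analysis of repeated measurements by ANOVA. It then says "All randomised participants will be included in the analyses". Neither this section nor any other names imputation, a likelihood-based model, a missing-data assumption or a sensitivity analysis.

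The same section sets success criteria that tolerate incomplete data. For Measurement 4, "we expect to have complete data (Measurement 4, completed at the final therapy session) of at least 70% of all participants included". For Measurement 5, "Complete three-month follow-up (Measurement 5, obtained via e-Box) of at least 50% of all participants included".

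On collection, section 3 (Referral procedure, step 5) says "When the therapist and client decide to end the treatment, the therapist asks the client to complete the final questionnaires", and Table 2 says of Measurement 4 "Questionnaire package is completed on tablet after last therapy session". Step 7 sets the follow-up date: "Three months after completing the 'End of treatment' assessment, the client will receive a questionnaire package in their e-Boks". Under Treatment completion, every client is expected to answer at three months about other help received. Section 6 lets a client leave treatment at any time and is silent on measurement afterwards.

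Two further facts bear on the remedy. Table 2 says of Measurement 2 "Questionnaire package is completed on tablet before randomisation and first therapy", so a pre-randomisation ITQ score should exist for every randomised client. The note to Table 2 adds that "measurement 3 occurs after each treatment module (including the intro module) and is thus carried out several times", and the ITQ is part of that package.

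**The concern.** The description of the analysis set and the named methods do not match. A client without Measurement 4 contributes nothing to the end-of-treatment t-test. Followed as written, the analyses cover available or complete cases but are described as covering everyone randomised. Someone using the pilot results to design the Phase III trial could take the end-of-treatment means for those of all 60 clients.

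The second part is a gap in data collection. Measurement 4 is tied to the last session or to a joint decision to end, and step 7 starts the three-month clock when Measurement 4 is completed. A client who simply stops coming triggers neither. Data collection is part of the pilot's first primary objective (section 2), so an undefined procedure for these clients bears on what the pilot is meant to assess.

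**Working it through.** **Inputs from the documents.** 30 clients per arm, 60 in all; floors of 70% at Measurement 4 and 50% at Measurement 5; 95% confidence level. The plan gives no SD, effect size or dropout forecast, so results are in SD units. The sample size rests on comparable feasibility studies rather than a formula; only the sum 30 + 30 = 60 can be reproduced.

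**Numbers at the floors.**
- Measurement 4: 60 × 0.70 = 42 observed, 18 missing.
- Measurement 5: 60 × 0.50 = 30 observed, 30 missing.
- If the ANOVA takes both time points and drops incomplete clients, the number left lies between 60 − 18 − 30 = 12 (no overlap in missingness) and 30 (full overlap).

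**Precision of the t-test.** Half-width = t(0.975, n1 + n2 − 2) × √(1/n1 + 1/n2).
- 30 and 30: 0.517 SD.
- 21 and 21: 0.624 SD, which is 21% wider.
- 24 and 18: 0.630 SD.

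**Bias.** Let p be the share missing in an arm and d the mean gap between clients with and without a score. The observed mean is off by p × d. Assume d of 0.25 to 1.0 SD, in either direction.
- Within an arm at 30% missing: 0.3 × 0.25 = 0.075 to 0.3 × 1.0 = 0.30 SD.
- Arm contrast with the same d in both arms, (p2 − p1) × d: 0 at 30% v 30%; 0.025 to 0.10 SD at 25% v 35%; 0.05 to 0.20 SD at 20% v 40%.

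**What a model with the pre-treatment score gains.** Take 30 pre-treatment and 21 Measurement 4 scores per arm, with assumed correlation r.
- SE of the t-test contrast: √(2/21) = 0.31 SD.
- SE with pre-treatment means constrained equal, √((2/21)(1 − r²)): 0.29, 0.27 and 0.22 SD at r = 0.3, 0.5 and 0.7.
- SE without the constraint, √(2[(1 − r²)/21 + r²/30]): 0.30, 0.30 and 0.29 SD.

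**How much dropout bias is removed.** Assumed correlations: pre-treatment with Measurement 4, 0.5; last module with Measurement 4, 0.8; pre-treatment with last module, 0.6. Missing 20% v 40%. The table gives large-sample bias of the Measurement 4 contrast in SD units.

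| Dropout driven by | Available cases | Pre-treatment score used | Pre-treatment and last module scores used |
|---|---|---|---|
| Last module score (leavers about 0.8 SD worse) | 0.14 | 0.09 | 0.00 |
| Unseen Measurement 4 score (leavers about 1.0 SD worse) | 0.18 | 0.14 | 0.07 |

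A rough hand check for the second row: the share removed is about r² = 0.25 with the pre-treatment score alone. With both scores, R² = 0.5 × 0.031 + 0.8 × 0.781 = 0.64. The table gives about 22% and 61%. The correction is real but partial, and module scores exist only for the ITQ among the outcome scales.

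**The case against.** The strongest reply is that little depends on this. Section 4 disclaims formal analysis, calls everything exploratory, and the primary objectives concern feasibility and resources. The disputed sentence can also be read as defining the population: nobody is set aside for ending early or not recovering. The same section expects incomplete Measurements 4 and 5, so the plan does not claim 60 observed scores. And the listwise point applies to a classical ANOVA, while the plan does not say which kind it means. All of this stands, and it limits the point to an ambiguous label and an unstated procedure.

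A reader might infer more than the documents support:
- *That the arm comparison is biased.* It is biased only if dropout, or its link to outcome, differs between arms, and nothing in the plan predicts that. Nor is the direction known: treatment may end on recovery, so some who leave could be doing better.
- *That the floors forecast dropout.* They are thresholds for success.
- *That clients without Measurement 4 are shut out of Measurement 5*, so that criterion 3 would need 30 of 42 (71%) to reply. Table 2 sends Measurement 5 by e-Boks without that condition, and Treatment completion expects all clients to respond. Only the date is undefined.
- *That all early endings are affected.* Agreed endings, including early responders, are covered by step 5. Step 6 also places Measurement 4 at end of treatment without requiring an agreed ending. The gap concerns clients who stop without a closing contact, and the documents do not say how many to expect.
- *That a Measurement 5 arm contrast suffers too.* With 15 per arm its half-width would be 0.75 SD, but the plan names a between-arm test only at end of treatment.

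**Conclusion.** The point holds in limited form. The statement about the analysis set does not fit the named methods, no missing-data method is given, and clients who stop attending without a closing contact have no stated route to Measurement 4 or date for Measurement 5.

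Its size at the 70% floor is 18 of 60 clients outside the t-test and a half-width of 0.62 SD rather than 0.52 SD. Within-arm change is biased if leavers differ from stayers; the range of 0.08 to 0.30 SD at 30% missing rests wholly on the assumed gap, and the sign is unknown. The illustrated arm-contrast bias, 0 to 0.20 SD, lies inside the confidence interval. The consequence is therefore not a wrong efficacy decision. It is an unclear analysis set in results meant to inform the Phase III trial, and an undefined step in the data collection that the pilot is to assess.

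**What to change.** **(a) Analysis.** For each scale, replace the t-test and separate ANOVAs by one exploratory linear mixed model over pre-treatment, Measurement 4 and Measurement 5, with arm-by-time and site (the randomisation stratifier). Constrain the pre-treatment mean to be equal across arms; this is justified because Measurements 1 and 2 precede randomisation. Use Measurement 2 as pre-treatment, or Measurement 1 for DASS-42 and PCL-C. Keep every randomised client with any score. Report the Measurement 4 contrast with its 95% CI and the number observed by arm and time point, and state that the correction for dropout is partial.

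For the ITQ, add a sensitivity analysis that uses the last available module score as an auxiliary variable for a missing Measurement 4, for example by multiple imputation within arm. A model on weeks since randomisation would not serve: treatment length varies, so Measurement 4 falls at a different week for each client and its contrast is not a defined time point.

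If the t-test is kept, say that available scores are analysed and report missing numbers by arm. That costs one sentence and one table row.

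**(b) Collection.** For clients who stop attending but have not withdrawn consent, send the Measurement 4 package by e-Boks, which already carries Measurements 1 and 5. When Measurement 4 is not completed, time Measurement 5 from the last session attended. Count mailed Measurement 4 replies separately, because criterion 2 refers to completion at the final session and would otherwise be inflated. As an illustration, assume that one third to all of the 18 are non-attenders and that 25% to 50% of them reply. The gain is then 18 × 1/3 × 0.25 = 1.5 to 18 × 0.5 = 9 scores; at 51 clients the half-width is 0.56 SD.

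**Cost.** Some SAP wording, slightly more analysis work, a mailing through an existing channel, and some Measurement 4 packages answered at home rather than on the tablet.

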5. TARGET GROUP/PARTICIPANTS

During the recruitment period, all veterans who turn to the MPD with CPTSD will be invited to participate in the study. Clients are selected to participate on the following in- and exclusion criteria:

Inclusion criteria

- Meets the diagnostic criteria for CPTSD, assessed with the ITQ
- Danish veteran (cf. the Veteran Policy of Denmark³)
- Seeks help for deployment-related psychological issues

Exclusion criteria

- Severely suicidal⁴
- Current alcohol or drug abuse that prevents treatment⁵
- Blast injuries or current severe attention disorder
- Has received psychotherapeutic treatment in the past three months
- Is participating in another research project⁶ that interferes with this research project

6. RISKS, SIDE EFFECTS AND SHORT- AND LONG-TERM DISADVANTAGES

No side effects are expected in the short or long term by participating in the psychotherapeutic MPC treatment programme, and no known side effects of similar psychotherapeutic interventions are described in the literature. In the case of side effects that do not go away within 1-2 therapy

³ According to the Veteran Policy of Denmark of 5 September 2016, a veteran is defined as 'a person who has been deployed in international operations at least once, on the grounds of a decision made by Folketinget, the Danish Government or a minister' regardless of whether they still serve in the military (<https://fmn.dk/temaer/veteraner/Documents/the-veteran-policy-of-denmark-2016.pdf>)

⁴ To a degree that will make it difficult to complete the manualised treatment programme

⁵ E.g. if the client shows up under the influence of intoxicants

⁶ For example, the client cannot simultaneously participate in other research projects in the Danish Veteran Centre, such as evaluation of body therapy with BBAT for PTSD.

sessions, the client will be offered other relevant treatment at the MPD. Any side effects are registered by the therapist. The client may always withdraw from the MPC treatment if they do not wish to continue, and the client is informed that this will not affect their possibilities of receiving other relevant psychological treatment at the MPD.

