As an integral part of the treatment, a short assessment is conducted after each treatment module by having the client complete the primary outcome measure, the International Trauma Questionnaire (ITQ; Cloitre et al., 2018), which is used as a measure for assessing ICD-11 PTSD and CPTSD. In practice, the client fills in the ITQ on a tablet in the beginning of the last session of each treatment module, after which the client and therapist receive an automatic response on the tablet, establishing whether the client (based on the ITQ) continues to meet the diagnostic criteria for PTSD or CPTSD. If the client has achieved sufficient symptom recovery and no longer meets the diagnostic criteria for CPTSD, the client is considered a treatment completer. However, the client and the therapist might decide to continue treatment until the client no longer meets the diagnostic criteria for PTSD. In this way, treatment can continue up till 32 therapy sessions but client and therapist can end the treatment earlier if the client has a valid assessment and falls out of CPTSD criteria.

After completing the MPC treatment, the client cannot receive psychological treatment at the Danish Veteran Centre, until a three-month follow-up of the treatment effect has been completed. However, after a three-month follow-up, the client is welcome to seek psychological treatment again at the Danish Veteran Centre. If deemed relevant, the client is offered help and support from the Counselling and Rehabilitation Department as well as from the Family Unit under the Danish Veteran Centre, independently of the MPC treatment programme. If a client is assessed to require psychological treatment before the three-month follow-up, this will be initiated. As part of the three-month follow-up, all clients respond to whether they have received other help and support from the Danish Veteran Centre or others after ending their MPC treatment.

Practical implementation

Treatment sites and participating therapists (will be updated regularly)

The treatment is carried out at five local veteran centres in Denmark by six clinical psychologists employed by the MPD, Danish Veteran Centre:

1. [name]. Clinical psychologists: [name] and [name].
2. [name]. Clinical psychologist: [name]
3. [name]. Clinical psychologist: [name]

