7. COLLECTION OF NEW BIOLOGICAL MATERIAL OR BIOLOGICAL MATERIAL FROM EXISTING BIOBANK

The project neither collects new biological material nor biological material from existing biobanks. The project is based on questionnaire data.

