8. DATA FROM PATIENT RECORDS

The project will not use data from patient records.

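### Harm recording rests on the treating therapist: no client item on unwanted effects is described, the register's destination is not stated, and clients who stop without Measurement 4 have no stated follow-up trigger

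*Combined protocol and SAP*

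**What the plan says.** **Recording of harm.** Section 6 states that no side effects are expected and then says "Any side effects are registered by the therapist". It gives no form, definition, timing or place of storage. Sections 6 and 14 add a rule for action: a client whose side effects persist past one or two sessions is offered a different treatment in the department. Section 3 (Record keeping) names COSMIC as the system in which treatment is recorded. Section 8 says "The project will not use data from patient records".

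**What clients report.** Table 2 lists 21 measures. Nearest to harm are the symptom scales and four suicidality questions, asked at Measurements 1, 4 and 5. During treatment, "the client fills in the ITQ on a tablet in the beginning of the last session of each treatment module", and client and therapist both see the result. Section 3 (Treatment completion) says that at the three-month follow-up "all clients respond to whether they have received other help and support"; the ten items of that measure are not reproduced.

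**Follow-up.** Section 3 (Referral procedure) says "Three months after completing the 'End of treatment' assessment, the client will receive a questionnaire package in their e-Boks". The success criteria in Section 4 ask for Measurement 4 from at least 70%, and Measurement 5 from at least 50%, of all those included.

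**Analysis.** Section 4 plans end-of-treatment comparisons of the ITQ and the secondary outcomes, within-group ANOVA and a simple compilation of the data. It names no summary of side effects or suicidality, and suicidality is not listed under the secondary outcomes.

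**The concern.** The therapist who registers side effects also delivers the allocated arm. Some of the therapists helped to develop the programme (Section 3, Treatment sites), and the protocol tells them to expect no side effects. This does not show that entries will be biased, but recording by that person alone has no independent check. A client report would be the natural one.

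The plan itself foresees that some clients will move to another treatment because of side effects. With no described item on the reason for ending, such exits cannot be told apart from other dropout in the questionnaire data.

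The first primary objective in Section 2 is to assess the trial process, including data collection, ahead of a Phase III trial. Harm that a client would have attributed to treatment but did not tell the therapist cannot be reconstructed later. The gap is widest for clients who leave without Measurement 4.

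**Working it through.** The plan states no harm figure to reproduce. The check is a comparison of the texts plus simple arithmetic.

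**1. Could Table 2 hold an undescribed item?** Sum of items in the marked rows against the stated total:

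| Measurement | Sum of marked rows | Stated | Difference |
|---|---|---|---|
| 1 | 142 | 142 | 0 |
| 2 | 96 | 106 | 10 |
| 3 | 20 + 24 + 6 = 50 | 57 | 7 |
| 4 | 184 | 237 | 53 |
| 5 | 184 | 184 | 0 |

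Measurements 1 and 5 reconcile, so no further item fits there. Measurements 2 to 4 do not. The text also gives four questionnaires at Measurement 3, where three are marked. The table may have been damaged in extraction, so I do not treat the differences as errors in the plan. At Measurement 4 the stated time of 30 minutes is already below the 33.6 minutes that the listed questionnaires sum to, so the time gives no sign of extra items. The supportable statement is that 0 of 21 measures, *as described*, ask about unwanted effects or the reason for ending.

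**2. Who can be missed.** With 60 clients:
- Without Measurement 4, at the limit of the criterion: 60 − 0.70 × 60 = 18.
- Without Measurement 5, at the limit: 60 − 0.50 × 60 = 30. At least 30 − 18 = 12 of these have Measurement 4, with its suicidality questions.
- If all 18 also lack a trigger for Measurement 5, at most 60 − 18 = 42 packages are sent. The 50% criterion then needs 30/42 = 71% of them returned, because its denominator is all 60.
- If the 18 split equally (an assumption), 9/30 = 30% of each arm has no client report at end of treatment.

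**3. How far the module-end ITQ reaches.** The introduction has 2 sessions and each module 6, so modules end at sessions 2, 8, 14, 20, 26 and 32. A client who stops after session 7 last completed the ITQ in session 2, leaving sessions 3 to 7, that is 5 sessions. In the control arm trauma processing is the fourth module, sessions 21 to 26. A client who leaves during it has a last ITQ from session 20, before it began.

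**4. What a descriptive table could show.** Exact (Clopper-Pearson) 95% intervals. For no events the upper limit is 1 − 0.025^(1/n).
- 0/30: 0% to 11.6%
- 3/30: 2.1% to 26.5%
- 6/60, arms pooled: 3.8% to 20.5%

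The counts are illustrative. Intervals this wide describe tolerability but would not separate the arms.

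**The case against.** The best case for the plan is that harm is watched in several ways. Therapists register side effects, and persistent ones lead to an offer of other treatment. In addition, "The participating therapists receive method-specific supervision in MPC every 14 days". The ITQ is repeated at module ends, suicidality is asked at three occasions, severely suicidal clients are excluded, and treatment can start before follow-up if needed. The results will be reported under CONSORT, and the compilation of pilot data could include side effects. No objective or success criterion concerns harm, and both arms receive the same components. All of this stands, and it limits the weight of the point. None of it is described as a client report of unwanted effects, and a reporting commitment cannot recover reports that were not collected.

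Some stronger readings are tempting but not supported:
- *The register is in COSMIC and therefore excluded.* Section 6 does not say where side effects are registered, so Section 8 bites only if they are in the patient record. That the therapist is the only recorder is likewise inferred from no one else being named.
- *Only questionnaires count as data.* The sentence "The project is based on questionnaire data" closes the section on biological material. The plan also needs staff time (Section 2) and acceptance rates (Section 4), so it is not an exhaustive list.
- *Harm collection is wholly untried.* Therapist registration and the suicidality questions are harm collection.
- *Everyone who ends early is lost to follow-up.* Measurement 4 is requested whenever client and therapist decide to end, so agreed early endings are covered. The follow-up text speaks of all clients. What is missing is a mechanism for those who stop without Measurement 4.

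**Conclusion.** The point holds as an optional, inexpensive improvement. It is not an error in a stated figure, and it does not threaten the pilot's feasibility aims.

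Three gaps stand on the text: no described client item on unwanted effects or on why treatment ended; no stated destination for the therapist's register and no named harm summary; and a follow-up clock that starts only when Measurement 4 is completed. The first and third carry most of the weight. The second alone would be missing detail.

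The size is bounded: up to 18 of 60 clients without Measurement 4, and up to 5 sessions after the last ITQ session for a client who leaves mid-module. These are limits, not expected losses. The conclusion assumes that the unexplained items in the extracted Table 2 do not include a question on unwanted effects, and that the unreproduced items on other help and support do not ask about them.

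**What to change.** 1. Add one short client item at Measurements 3, 4 and 5: any unwanted effect or worsening the client attributes to treatment, and whether it is still present.
2. Have the therapist enter side effects and the reason for ending on the trial tablet for every client, including those who leave without Measurement 4. This settles the route into the data set without using patient records.
3. For clients without Measurement 4 who have not withdrawn consent, send the Measurement 5 package three months after the last attended session.
4. In Section 4, commit to a descriptive table, overall and by arm, with exact 95% intervals and no test: side effects (client- and therapist-reported separately), endings due to them, and suicidality.

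Sample size, randomisation and treatment are unchanged. The cost is about a minute per occasion, a changed e-Boks date for at most 18 clients if the 70% criterion is met, and one more table. Response from clients who have left is likely to be low, and the intervals will be wide.
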